# 3.1.1 COVID-19 Contingency Measures

In cases of COVID-19 limitations, it is the Investigator's responsibility to assure the safety of participants. If necessary, the Sponsor will implement and document mitigation strategies. It may be necessary to conduct some study visits virtually. At the Investigator's discretion, the study visit(s) can be conducted in-clinic or virtually. If conducted virtually, the visit will include alternative methods for safety, efficacy, and distribution/collection of study drug, including but not limited to phone/video contact, alternative location for biologic sample collection, alternative

secure delivery of study drug, home health care (if available), and a secured way of transferring participant data from and to home health services and the site.

If these contingency measures occur, the Sponsor will document the changes made, communicate recommendations about such changes in a timely fashion to minimize or prevent disruptions to the study, and support sites in implementing these changes. Documentation of these cases and the site's management of participants should be recorded in the Investigator study files. In the absence of a COVID-19 impact, it is expected that Investigators and participants follow the protocol requirements as set forth.

# 3.2 Study Indication

Obicetrapib is being developed as an adjunct to diet and maximally tolerated lipid-modifying therapy for the treatment of adults with HeFH or a history of ASCVD who require additional lowering of LDL-C.

#### 4 SELECTION AND WITHDRAWAL OF PARTICIPANTS

# 4.1 Inclusion Criteria

Participants who meet all of the following criteria will be eligible to participate in the study:

- 1. Are willing and able to give written informed consent before initiation of any study-related procedures and willing to comply with all required study procedures;
- 2. Are male or female and  $\geq 18$  years of age at Screening (Visit 1);
  - o Females may be enrolled if all 3 of the following criteria are met:
    - They are not pregnant;
    - They are not breastfeeding; and
    - They do not plan on becoming pregnant during the study.
  - Females of childbearing potential must have a negative urine pregnancy test at Screening (Visit 1);

Note: Females are not considered to be of childbearing potential if they meet 1 of the following criteria as documented by the Investigator:

- They have had a hysterectomy or tubal ligation at a minimum of 1 cycle prior to signing the ICF; or
- They are postmenopausal, defined as ≥1 year since their last menstrual period for females ≥55 years of age or ≥1 year since their last menstrual period and have a follicle-stimulating hormone level in the postmenopausal range at Screening (Visit 1) for females <55 years of age.

- Females of childbearing potential must agree to use an effective method of avoiding pregnancy from Screening (Visit 1) until 35 days after the last dose of study drug. Males whose partners are of childbearing potential must agree to use an effective method of avoiding pregnancy from Screening (Visit 1) until 35 days after the last dose of study drug. Effective methods of avoiding pregnancy are contraceptive methods used consistently and correctly (including implantable contraceptives, injectable contraceptives, oral contraceptives, transdermal contraceptives, intrauterine devices, and barrier methods) or a sterile sexual partner.
- 3. Have underlying HeFH and/or a history of ASCVD;

#### Diagnosis of HeFH:

Diagnosis must be made by either prior historical genotyping or by clinical assessment using either the WHO Criteria/Dutch Lipid Clinic Network Criteria with a score that is ≥3 points, as specified in Appendix C, or the Simon Broome Register Diagnostic Criteria with an assessment of "Possible HeFH" or "Definite HeFH," as specified in Appendix D. 17,18 LDL-C values are required to assess the Dutch Lipid Clinic Network Criteria and/or Simon Broome Register Diagnostic Criteria. In some cases, historical lipid values may not be obtainable, as participants may have initiated lipid-modifying therapies years prior. In these instances, the Investigator will need to estimate an "off-treatment" LDL-C value to calculate whether the participant qualifies for the study. For this purpose, Appendix E contains correction factors for a variety

of statins and/or ezetimibe. The current LDL-C value obtained most recently and/or through the screening process can be converted using the appropriate correction factor. This value will be used to assess whether the participant meets either the Dutch Lipid Clinic Network Criteria or the Simon Broome Register Diagnostic Criteria. Participants with a diagnosis of HeFH may or may not have a history of ASCVD or ASCVD-risk equivalents;

History of ASCVD, defined by at least 1 of the following conditions:

- o Coronary artery disease:
  - MI;
  - Prior coronary revascularization (percutaneous coronary intervention [PCI] or coronary artery bypass grafting [CABG]);
  - Angiographic or computed tomography (CT) imaging (eg, multidetector CT or CT angiography) evidence of coronary atherosclerosis with >70% stenosis in at least 1 major epicardial coronary artery; or
  - Coronary calcium score >100 Agatston units within 6 months prior to Screening (Visit 1).
- o Cerebrovascular disease:
  - Prior ischemic stroke confirmed by a brain imaging study (CT or magnetic resonance imaging), considered not to be caused by atrial fibrillation, valvular heart disease, or mural thrombus;
  - Carotid artery stenosis >70% on prior angiography or ultrasound; or
  - History of percutaneous or surgical carotid artery revascularization.
- o Peripheral arterial disease:
  - Prior documentation of a resting ankle-brachial index  $\leq 0.85$ ;
  - History of percutaneous or surgical revascularization of an iliac, femoral, or popliteal artery; or
  - Prior non-traumatic amputation of a lower extremity due to peripheral artery disease.
- 4. Are on maximally tolerated lipid-modifying therapy as an adjunct to a lipid-lowering diet and other lifestyle modifications, defined as follows:
  - o A statin at a maximally tolerated stable dose;
    - A participant's maximally tolerated stable statin dose will be determined by the Investigator using his/her medical judgment and available sources, including the participant's self-reported history of lipid-modifying therapy for at least 8 weeks prior to Screening (Visit 1); and

For any participant not taking statin therapy due to statin intolerance, including those participants taking bempedoic acid or fibrate monotherapy, written confirmation will be required of both the participant and the Investigator stating that the participant was statin intolerant, aware of the benefit of statins to reduce the risk of a MACE, and aware that many other patients who are unable to tolerate a statin were actually able to tolerate a different statin or dose.

Note: Statin intolerance will be defined as intolerance due to an adverse safety effect that started or increased during statin therapy and resolved or improved when statin therapy was discontinued, resulting in an inability to tolerate either 1) two or more statins at any dose, or 2) one statin at any dose and either an unwillingness to attempt a second statin or advice by a physician not to attempt a second statin.

- Ezetimibe for at least 8 weeks with or without maximally tolerated statin prior to Screening (Visit 1);
- Bempedoic acid for at least 8 weeks in combination with a maximally tolerated statin prior to Screening (Visit 1); and/or
- A PCSK9-targeted therapy alone or in combination with other lipid-modifying therapy for at least 4 stable doses prior to Screening (Visit 1).

Note: At least 70% of the participants enrolled into this study must be taking HIS. Documentation in the electronic case report form (eCRF) of the reason why a participant is unable to take HIS is required. HIS include the following: atorvastatin 40 and 80 mg and rosuvastatin 20 and 40 mg.

- 5. Have a fasting serum LDL-C at Screening (Visit 1) as follows:
  - Have a fasting serum LDL-C  $\geq$ 55 mg/dL ( $\geq$ 1.4 mmol/L) to <100 mg/dL (<2.6 mmol/L) OR non-HDL-C  $\geq$ 85 mg/dL ( $\geq$ 2.2 mmol/L) to <130 mg/dL (<3.4 mmol/L) with at least 1 of the following risk enhancers:
    - Recent MI (>3 and <12 months prior to Randomization [Visit 2]);
    - Type 2 diabetes mellitus;
    - Current daily cigarette smoking;
    - Age of >60 years;
    - High sensitivity C-reactive protein (hsCRP) ≥2.0 mg/L (≥19.0 nmol/L) at Screening (Visit 1) or within 6 months prior to Screening (Visit 1);
    - Fasting TG >150 mg/dL (>1.7 mmol/L);
    - Fasting Lp(a) > 30 mg/dL (>70 nmol/L); and/or
    - Fasting HDL-C <40 mg/dL (<1.0 mmol/L).

#### OR

Have a fasting serum LDL-C ≥100 mg/dL (≥2.6 mmol/L) OR non-HDL-C ≥130 mg/dL (≥3.4 mmol/L).

Note: LDL-C at Screening (Visit 1) will be calculated using the Friedewald equation unless TG  $\geq$ 400 mg/dL ( $\geq$ 4.5 mmol/L) or LDL-C  $\leq$ 50 mg/dL ( $\leq$ 1.3 mmol/L). If TG  $\geq$ 400 mg/dL ( $\geq$ 4.5 mmol/L) or LDL-C  $\leq$ 50 mg/dL ( $\leq$ 1.3 mmol/L), then LDL-C level will be measured directly by preparative ultracentrifugation, also referred to as beta quantification.

- 6. Have fasting TG <500 mg/dL (<5.7 mmol/L) at Screening (Visit 1); and
- 7. Have an estimated glomerular filtration rate (eGFR) ≥30 mL/min/1.73 m² calculated using the Chronic Kidney Disease Epidemiology Collaboration equation at Screening (Visit 1).

#### 4.2 Exclusion Criteria

Participants who meet any of the following criteria will be excluded from participation in the study:

- 1. Have current or any previous history of New York Heart Association class III or IV HF or left ventricular ejection fraction <30%;
- 2. Have been hospitalized for HF within 5 years prior to Screening (Visit 1);
- 3. Have had any of the following clinical events within 3 months prior to Screening (Visit 1):
  - o Non-fatal MI;
  - Non-fatal stroke;
  - o Non-elective coronary revascularization; and/or
  - O Hospitalization for unstable angina and/or chest pain.
- 4. Have uncontrolled severe hypertension, defined as either systolic blood pressure ≥160 mmHg or diastolic blood pressure ≥100 mmHg prior to Randomization (Visit 2) taken as the average of triplicate measurements. One triplicate retest will be allowed during the same visit, at which point if the retest result is no longer exclusionary, the participant may be randomized;
- 5. Have a formal diagnosis of homozygous FH;
- 6. Have active liver disease, defined as any known current infectious, neoplastic, or metabolic pathology of the liver; unexplained elevations in alanine aminotransferase (ALT) or aspartate aminotransferase (AST) >3 × upper limit of normal (ULN); or total bilirubin >2 × ULN at Screening (Visit 1);
  - Note: An abnormal ALT, AST, or total bilirubin must be confirmed by a repeat abnormal measurement at least 1 week apart.
- 7. Have HbA1c ≥10.0% (≥0.100 hemoglobin fraction) or a fasting glucose ≥270 mg/dL (≥15.0 mmol/L) at Screening (Visit 1);
- 8. Have thyroid-stimulating hormone  $\geq 1.5 \times ULN$  at Screening (Visit 1);
- 9. Have creatine kinase (CK)  $>3 \times$  ULN at Screening (Visit 1);
- 10. Have a history of a malignancy that required surgery (excluding local and wide local excision), radiation therapy, and/or systemic therapy during the 3 years prior to Randomization (Visit 2);
- 11. Have a known history of alcohol and/or drug abuse within 5 years prior to Randomization (Visit 2);

- 12. Have received treatment with other investigational products or devices within 30 days of Screening (Visit 1) or 5 half-lives of the previous investigational product, whichever is longer; Note: Participants who have received treatment for COVID-19 with standard of care and/or emergency use authorization medications, including vaccinations and boosters, within 30 days of Screening (Visit 1) or 5 half-lives of the previous investigational product will be permitted.
- 13. Are taking gemfibrozil or have taken gemfibrozil within 30 days of Screening (Visit 1);
- 14. Have planned use of other investigational products or devices during the course of the study;
- 15. Have participated in any clinical study evaluating obicetrapib;
- 16. Have a known allergy or hypersensitivity to the study drug, placebo, or any of the excipients in the study drug or placebo; or
- 17. Have any participant condition that, according to the Investigator, could interfere with the conduct of the study, such as, but not limited to, the following:
  - o Are unable to communicate or to cooperate with the Investigator;
  - Are unable to understand the protocol requirements, instructions and study-related restrictions, and the nature, scope, and possible consequences of the study (including participants whose cooperation is doubtful due to drug abuse or alcohol dependency);
  - Are unlikely to comply with the protocol requirements, instructions, and study-related restrictions (eg, uncooperative attitude, inability to return for follow-up visits, and improbability of completing the study);
  - Have any medical or surgical condition which, in the opinion of the Investigator, would put the participant at increased risk from participating in the study; or
  - o Are directly involved in the conduct of the study.

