## 5.3 Randomization and Blinding

Participants who meet all inclusion criteria and none of the exclusion criteria will be randomized on Day 1 (Visit 2) via the Interactive Response Technology (IRT) system in a 2:1 ratio to receive obicetrapib or placebo.

Treatment allocation will be stratified based on CV risk (HeFH or non-HeFH) and Baseline statin dose (HIS or non-HIS). At least 70% of the participants enrolled into this study must be taking HIS. Participants with underlying HeFH but without a history of ASCVD will comprise up to a maximum of 20% of the total participants enrolled into the study.

The study drug blind will be maintained through the EOS Visit (Visit 8). Participants, the Sponsor, Investigators, and all study site personnel involved in the study, including personnel carrying out study procedures, evaluating participants, entering study data, and/or evaluating study data, will remain blinded to treatment allocations until all participants have completed the EOS Visit assessments and the database has been locked for analysis.

Active and placebo product will be identical. Medication bottles with a unique code will be assigned to participants at various points in the study by the IRT system.

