#### 5.6.2 Restricted Medications and/or Procedures

Participants receiving lipid-modifying therapies as described in Section 4.1 (Inclusion Criterion 4) should be on a stable dose for at least 8 weeks prior to Screening (Visit 1). Participants taking PCSK9-targeted therapies should have received 4 stable doses prior to Screening (Visit 1). There should be no planned medication or dose changes of lipid-modifying therapy during study participation. Participants must agree not to initiate any new lipid-modifying medications (including supplements) and not to change the dose of the existing lipid-modifying medications (including supplements) during study participation. However, if there are changes to lipid-modifying therapy during the study, these data will be recorded.

Participants are not required to be taking statins. Reasons for not using statin therapy must be documented (eg, the participant is statin intolerant) as described in Section 5.6.3. If the participant is statin intolerant, written confirmation will be required of both the participant and the Investigator stating that the participant was statin intolerant, aware of the benefit of statins to reduce the risk of a MACE, and aware that many other patients who are unable to tolerate a statin were actually able to tolerate a different statin or dose. Statin intolerance, as defined in Inclusion Criterion 4, should be recorded as intolerance to any dose of any statin as historical events attributed to the statin in question, in the source documentation and eCRF as part of the medical history to confirm intolerance to statins.

Participants must agree not to donate blood during study participation.

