## **APPENDIX A: SCHEDULE OF PROCEDURES**

	Screening			Treatn	nent Period			EOS 
Visit	V1	V2	V3	V4	V5	V6	V7/EOT/ET 	V8
								35 days after
Study Day		1	30	84	180	270	365	last dose
Window (±days)			±3	±7	±7	±7	±7	±7
Informed consent 	X							
Assessment of eligibility	X 	$X^4$						
Demographics and medical history	X							
Pregnancy test, FSH 	X	X			X		X	
TSH	X							
Randomization		X						
Study drug administration		X	X	X	X	X	X	
Physical examination 	X						X	
Weight, height, and BMI	X 						X	
Vital signs 	X	X	X	X	X	X	X	X
24-hr ABPM 	$X^{10}$					X 		
12-lead ECG 		X					X	
Lipid profile/biomarkers (fasting) 	X	X	X	X	X	X	X	
Serum archive sample for future								
assessment of biomarkers related to								
dyslipidemia and/or CV risk (fasting) 		X					X	
UACR, UPCR (fasting) 		X					X	
Aldosterone, hsCRP (fasting) 	$X^{16}$	X					X	
Lp(a), ApoA1 (fasting) 	X	X		X				
Insulin for HOMA-IR (fasting) 	X	X		X	X	X	X	
Full serum chemistry (fasting) 		X			X		X	
Limited serum chemistry (fasting) 	X		X	X		X		
Urine dipstick analysis 	X	X					X	
Hematology and coagulation (fasting) 	X	X			X		X	
PK sample (central) 		X			X		X	
Prior/concomitant medications	X	X	X	X	X	X	X	X
Study drug dispensation		X	X	X	X	X		

Footnotes are at the end of the table.

	Screening		Treatment Period			EOS 		
Visit	V1	V2	V3	V4	V5	V6	V7/EOT/ET 	V8
St. I. D	20.4 1		20	0.4	100	250	265	35 days after
Study Day	-28 to -1	1	30	84	180	270	365	last dose
Window (±days)			±3	±7	±7	±7	±7	±7
Study drug return/compliance calculations			X	X	X	X	X	
CV events assessment 	X	X	X	X	X	X	X	X
AEs assessment	X	X	X	X	X	X	X	X

- 1. The onsite EOS Visit will include an assessment of vital signs, concomitant medications, CV events, and AEs will be completed and documented in the participant's record.

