3 STATISTICAL METHODOLOGY

3.1 General Considerations

3.1.1 Analysis Day

Analysis day will be calculated from the date of first dose of study drug. The day of the first dose of study drug will be Day 1, and the day immediately before Day 1 will be Day -1. There will be no Day 0.

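### Exclusions 2 and 3 look back only from Screening, so a listed cardiovascular event in the up to 28 days before Randomization generally meets no event-specific exclusion

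*Protocol*

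**What the plan says.** Protocol Section 4.2 (repeated in the Synopsis) sets two look-back exclusions for recent cardiovascular events.

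- Exclusion 3: "Have had any of the following clinical events within 3 months prior to Screening (Visit 1". The events are non-fatal MI, non-fatal stroke, non-elective coronary revascularization, and admission for unstable angina or chest pain.
- Exclusion 2: "Have been hospitalized for HF within 5 years prior to Screening (Visit 1".

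The schedule (Protocol Appendix A; SAP Table 1) places Screening on Days -28 to -1. Under Protocol Section 5.3 participants "will be randomized on Day 1 (Visit 2) via the Interactive Response Technology (IRT) system". The schedule row "Assessment of eligibility" is marked at both Visit 1 and Visit 2.

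Other look-back rules use the later visit. Exclusions 10 (malignancy) and 11 (alcohol or drug abuse) count back from Randomization. So does one of the risk enhancers in Inclusion Criterion 5: "Recent MI (>3 and <12 months prior to Randomization [Visit 2".

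**The concern.** Recent-event exclusions exist to keep people out shortly after the event. Here the clock stops at Visit 1, and someone who has one of the listed events while waiting for Visit 2 has not had it before Screening. The Visit 2 eligibility check does not help, because it re-applies wording that still refers to Visit 1.

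Two things are at stake. First, the participants whom the sponsor chose to exclude by name can be randomized days after the event unless the investigator decides otherwise. Second, the exploratory cardiovascular endpoints are timed from Randomization (Protocol Section 7). An index event just before time zero could be followed by a recurrence or revascularization that counts as a post-randomization endpoint.

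**Working it through.** The plan gives no event rate and no figure of its own on this point, so the check is one of dates and wording, followed by an upper bound on size.

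**1. Length of the gap.** Screening may fall as early as Day -28 and Randomization is Day 1. SAP Section 3.1.1 states "There will be no Day 0", so the interval from Day -28 to Day 1 is 28 days.

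**2. Two infarctions compared, with Visit 1 on Day -28.**

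| MI date | Relative to Visit 1 | Relative to Randomization | Exclusion 3 |
|---|---|---|---|
| Day -35 | 7 days before | 35 days before | Met: excluded |
| Day -10 | 18 days after | 10 days before | Not met |

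The more recent event is the one that passes. Section 4.4 uses Screening in the sense of a period, but reading it that way changes nothing: an event inside a period is not prior to it.

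**3. Whether another criterion catches the Day -10 event.**

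- Inclusion Criterion 5: this MI is too recent to serve as the risk enhancer. The participant can still enter on another enhancer, or with none if LDL-C is at least 100 mg/dL or non-HDL-C at least 130 mg/dL.
- Exclusion 1: it covers NYHA class III/IV heart failure or an ejection fraction below 30%, current or past, with no Screening anchor. It would catch some heart-failure admissions. It does not address MI, stroke, revascularization or unstable angina as such.
- Exclusion 17: it can stop any case, but on the investigator's opinion. It names neither an event nor a window.
- Nothing else in either document bars randomization because of an event between the two visits.

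**4. Upper bound on numbers.** Inputs: approximately 2400 randomized (Protocol Section 5.1), 28 days, and assumed annual rates for the listed events.

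Exposure = 2400 × 28/365 = 184 person-years.

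| Assumed rate per year | Events = 184 × rate |
|---|---|
| 1% | 1.8 |
| 3% | 5.5 |
| 5% | 9.2 |
| 9% | 16.6 |

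This is a ceiling at each rate. It gives everyone the full 28 days and supposes that everyone affected attends Visit 2 and passes exclusions 1 and 17.

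**5. Effect on the primary analysis.** With the plan's SD of 15% and 2280 evaluable participants split 2:1 (1520 and 760), the standard error of the difference is 15 × √(1/1520 + 1/760) = 0.666 percentage points. Take the top figure, 17/2400 = 0.7%, and assume those participants have twice the SD. The variance is multiplied by 1 + 0.007 × (4 − 1) = 1.021 and the standard error by about 1.01, giving 0.673. Against a planned effect of 30% this is immaterial.

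**The case against.** The strongest reply is that the gap is one of wording and that safeguards surround it. Cardiovascular events are reported from consent onward (Section 8.1) and assessed at Visits 1 and 2, so the investigator will know of the event. Randomizing that person then requires a judgement that exclusion 17 does not apply. All of that stands, and it will stop some cases. It remains discretionary, where the same event a few weeks earlier is barred outright.

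The reply also corrects several stronger readings that a reader might infer.

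- *That exclusion 17 is the only backstop.* It is not. Exclusion 1 carries no Screening anchor and covers part of the heart-failure limb, which is therefore the weaker part of this point.
- *That the anchors contradict each other.* They do not. An MI more than 3 months before Screening is also more than 3 months before Randomization, so the enhancer and exclusion 3 can both be applied. They are inconsistent in reference date, not incompatible. Exclusions 6 to 9, 12 and 13 are also tied to Screening.
- *That exclusion 4 is a precedent.* Its text, "diastolic blood pressure ≥100 mmHg prior to Randomization (Visit 2) taken as the average of triplicate measurements", describes a measurement and not a look-back window. The relevant comparators are exclusions 10 and 11 and the MI enhancer.
- *That a change of lipid therapy during screening is left open in the same way.* Section 5.6.2 says participants "should be on a stable dose for at least 8 weeks prior to Screening (Visit 1", which is again a Visit 1 anchor. But Inclusion Criterion 4 is in the present tense, and Section 5.6.2 also requires agreement not to start or alter such therapy during participation. Recording any changes is additional to that.
- *That the documents show a specific hazard of the drug after an acute event.* They show none. Section 4.3 says participants should not be taken off study drug or out of the study after a potential cardiovascular event. The protection argument rests only on the sponsor having named these events as exclusions.

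**Conclusion.** The point holds as a gap in two eligibility rules, with a perverse result at the boundary. For up to 28 days before Randomization, the events in exclusion 3 meet no event-specific exclusion, and neither does a heart-failure hospitalization that falls outside exclusion 1.

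The size is small: about 2 to 17 participants at most, or up to 0.7% of those randomized. That range rests on assumed rates of 1% to 9% per year, since the documents give none, and shorter screening would reduce it.

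A reader might infer that the primary result is at risk; the arithmetic does not support that. Allocation is randomized and double-blind, so neither arm is favoured, and the loss of precision is about 1% even under an unfavourable assumption. The cardiovascular endpoints are exploratory with nominal p-values, so a few early events linked to a screening-period event would matter for interpretation, not for a confirmatory claim. The reason to act is participant protection and the consistency of the criteria, at very low cost.

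**What to change.** Reconcile the reference dates of exclusions 2 and 3, in Section 4.2 and the Synopsis, with the criteria already anchored to Randomization. The Visit 2 eligibility check should then explicitly cover the listed events occurring between Visit 1 and Randomization. The sponsor's own events and window lengths stay as they are. If the Visit 1 anchor is deliberate, the protocol should say so and state how an event during screening is handled.

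No new assessment is needed, because cardiovascular events are already collected at both visits. The cost is a wording amendment and a few late screen failures, who may be rescreened under Section 4.5. The sample size and the analysis do not change.
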